Comparator products:	US-licensed Humira, solution for s.c. injection in single-use prefilled syringe (40 mg)		
dose:	Starting 1 week after a first administration of 80 mg Humira after randomization, patients will receive 40 mg every other week via a single prefilled glass syringe.		
mode of administration:	Subcutaneous injection		
Duration of treatment:	Patients are planned to be treated with trial medication for 24 weeks. Seven days after a first 80 mg administration of either BI 695501 or US-licensed Humira, patients will receive 40 mg of either BI 695501 or US-licensed Humira every other week up to efficacy assessment at Week 16. Only patients achieving at least a PASI 50 response will continue the treatment after 16 weeks, ending at Week 24.		
Endpoints	
Efficacy endpoints will be measured at Week 16 (equivalence assessment) and Week 24.
 
Primary efficacy endpoint:
 
 Proportion of patients with a 75% reduction in Psoriasis Area and Severity Index (PASI 75) response at Week 16 
Secondary endpoints:
 
Efficacy
 
 Proportion of patients with a PASI 75 response at Week 24 Mean percentage improvement in PASI at Week 16 Proportion of patients with a sPGA ≤ 1 (clear or almost clear) at Week 16 Proportion of patients achieving a Dermatology Life Quality Index (DLQI) of 0 or 1 at Week 16 
Safety
 
 Proportion of patients with drug-related adverse events (AEs) 		
Safety criteria:	Physical examination, vital signs (blood pressure, pulse rate, body temperature), 12-lead electrocardiogram (ECG), laboratory tests, continuous AE monitoring, and local tolerability.		
Statistical methods:	
Primary analysis
 
To conclude equivalence, the 95% confidence interval (CI) of the difference in PASI 75 response rate at Week 16 between BI 695501 and Humira must be fully
		

Name of company:		Boehringer Ingelheim	
Name of finished product:		NA	
Name of active ingredient:		BI 695501	
Protocol date: 26 Apr 2016	Trial number: 1297.12		Revision date:
		within the equivalence limits of $\pm 18\%$. Secondary analysis For the secondary efficacy endpoints, point estimates (risk difference for binary endpoints) and CIs will be calculated, but will be interpreted in a descriptive manner. Safety endpoints and AESIs will be presented descriptively. Risk ratio together with 95% CI will be presented for the secondary safety endpoint.	

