15.1.3.1. Calculation of difference in proportion (STEP 2 details)

The Week 16 endpoint will be analyzed using (M1) model.

The following SAS code will be used:

```
proc genmod data=data_PASI75_week_16 descend;
  class PASI75(ref="N") TRTP(ref="HUMIRA") EXPOS_BIO(ref="N") /
  param=GLM;
  model PASI75=TRTP BASELINE_PASI EXPOS_BIO/ dist=binomial link=logit;
  lsmeans TRT / ilink OBSMARGINS diff=all;
run;
```

The population adjusted natural scaled proportion at Week 16 are the estimates produced by the LSMEANS statement.

Document: \\eedc-nas01a:\Boehringer_Ingelheim\BI_695501\XXA39605\Biostatistics\Documentation\SAP\15-v2.0\BI 1297.12 SAP v2.0 31JAN2018.docx

Author: Version Number: 2.0
Version Date: 31JAN2018

Template No: CS_TP_BS016 Revision 4
Effective Date: 01Apr2016

Reference: CS_WI_BS005

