16. SAFETY OUTCOMES

All outputs for safety outcomes will be based on the SAF for overall and Period 1 outputs.

There will be no statistical comparisons between the treatment groups for safety data, unless otherwise specified with the relevant section.

Safety will be assessed as a secondary objective in this trial.

The safety endpoint is defined as the proportion of subjects with drug-related AEs. This safety endpoint is considered a secondary endpoint in this trial.

Other safety endpoints are:

- Proportion of patients with AEs, SAEs, and AESIs

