16.1.1.2. Risk ratio

Risk ratios and associated 95% exact confidence interval will be presented for adverse events of special interest.

Risk ratio will be defined as: $[a/(a+b)]/[c/(c+d)]$

where:

1. **a** is the number of subjects with AESI within treatment group BI 695501
2. **a+b** is the total number of subjects in treatment group BI 695501
3. **c** is the number of subjects with AESI within treatment Humira
4. **c+d** is the total number of subjects in treatment group Humira

PROC FREQ with option RELRISK will be used for programming purpose.

```
proc freq data=data_AESI;  
    tables AESI_WITH_CRITERION*TRT;  
    exact relrisk(method=score);  
    weight count;  
run;
```

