- The first letter of a text entry should be capitalized
- Listings of adverse events, concomitant medications, medical histories etc. should be sorted in chronological order, with earliest adverse event, medication or history coming first.
- The trial drug should appear first in tables with treatments as columns
- In general, only present totals (across treatment groups) at baseline/randomization, and do not present them post randomization.
- If possible, include 100% frequencies in the table shell, so that it is clear what the denominator is for percentage calculations.
- All listing outputs should be sorted (preferably by Treatment, Site Number and Subject Number).
- Do not use superscripts and subscripts
- The width of the entire output should match the linesize option

Univariate Statistics:

- Statistics should be presented in the same order across tables (i.e., n, Mean, SD, Median, IQR, Minimum, Maximum or n, gMean, gCV, Mean, CV, SD, Median, Minimum, Maximum)
- Table statistics should line up under the N part of the (N=XXX) in the table header. All decimal points should line up. If the minimum and maximum are output on one line as Minimum, Maximum then the comma should line up with the decimal point.
- If the original data has N decimal places, then the summary statistics should have the following decimal places:
 - Minimum and maximum: N
 - Mean, gMean, median, gCV% and CV%: N + 1
 - SD, IQR: N + 2

Frequencies and percentages (n and %):

- Percent values should be reported inside parentheses, with one space between the count and the left parenthesis of the percentage. Parentheses should be justified to accept a maximum of 100.0 as a value and padded with blank space if the percent is less than 100.0. An example is given below:

77 (100.0%)
50 (64.9%)
0 (0.0%)

- Percentages will be reported to one decimal place, except percents <100.0% but >99.9% will be presented as '>99.9%' (e.g., 99.99% is presented as >99.9%); and percents < 0.1%

Document: \\eedc-nas01a:\Boehringer_Ingelheim\BI_695501\XXA39605\Biostatistics\Documentation\SAP\15
-v2.0\BI 1297.12 SAP v2.0 31JAN2018.docx

Author:

Version Number:

2.0

Version Date:

31JAN2018

Template No: CS_TP_BS016 Revision 4

Reference: CS_WI_BS005

Effective Date: 01Apr2016

Statistical Analysis Plan

will be presented as '<0.1%' (e.g., 0.08% is presented as <0.1%). Rounding will be applied after the <0.1% and >99.9% rule.

E.g., (<0.1%)
(6.8%)
(>99.9%)

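### The AESI risk-ratio code in SAP 16.1.1.2 puts AESI status in the rows, so it does not compute the risk ratio that the section defines

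*SAP*

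**What the plan says.** SAP 16.1.1.2 states that "Risk ratios and associated 95% exact confidence interval will be presented for adverse events of special interest". It then gives the formula: "Risk ratio will be defined as: $[a/(a+b)]/[c/(c+d" and so on, with a and c the numbers of subjects with an AESI on BI 695501 and Humira, and a+b and c+d the treatment-group totals. Each proportion therefore has a treatment arm as its denominator.

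For implementation, "PROC FREQ with option RELRISK will be used for programming purpose". The table request in the code is "tables AESI_WITH_CRITERION*TRT", followed by a request for exact score-based limits for the relative risk. Nothing in the code transposes the table or sets the order of the levels.

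On the scope of the risk ratio, the protocol synopsis says: "Risk ratio together with 95% CI will be presented for the secondary safety endpoint". SAP 16 identifies that endpoint: "The safety endpoint is defined as the proportion of subjects with drug-related AEs". The text of SAP 16.1.1.2 applies the risk ratio to AESIs only.

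**The concern.** In a PROC FREQ two-way request the first variable forms the rows and the second the columns, and RELRISK takes row 1 over row 2. This is standard behaviour of the procedure; the SAP does not describe it. With AESI status in the rows, the denominators become the numbers of subjects with and without an AESI instead of the numbers in each arm. The formula and the code in one section then describe different quantities.

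The AESI groups are serious infections, hypersensitivity reactions, drug-induced liver injury and anaphylactic reactions (SAP 16.1.6), and comparing safety is a stated secondary objective. If the code were run as written, an imbalance in these events would be reported with the wrong size. Under some level orders it would also point the wrong way.

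**Working it through.** The documents give no AESI counts or risk ratios, so there is no plan figure to reproduce. The check applies the formula and the code to the same 2x2 counts.

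**Inputs**
- From the documents: about 300 patients randomized 1:1 (protocol synopsis), taken as 150 per arm; the definition and code in SAP 16.1.1.2.
- Assumed: the AESI counts, a on BI 695501 and c on Humira, with b = 150 − a and d = 150 − c.

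**Formulas**
- Defined ratio: (a/150)/(c/150).
- Code, Yes row first, BI 695501 column: [a/(a+c)]/[b/(b+d)].
- Code, No row first, BI 695501 column: the inverse of the line above.

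**Worked case, 6 versus 2**
- Defined: (6/150)/(2/150) = 3.00.
- Code, Yes first: (6/8)/(144/292) = 0.750/0.493 = 1.52. No first: 1/1.52 = 0.66.
- Humira column: (2/8)/(148/292) = 0.49, or 2.03 with No first.

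None of the four arrangements gives 3.00.

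**Other counts** (BI 695501 column; brackets are asymptotic 95% score limits, and the SAP's exact limits will differ)

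| AESIs, BI vs Humira | Defined ratio | Code, Yes row first | Code, No row first |
|---|---|---|---|
| 8 vs 4 | 2.00 (0.66 to 6.14) | 1.35 (0.78 to 1.82) | 0.74 (0.55 to 1.28) |
| 6 vs 2 | 3.00 (0.71 to 12.9) | 1.52 (0.82 to 1.97) | 0.66 (0.51 to 1.22) |
| 10 vs 2 | 5.00 (1.26 to 20.1) | 1.71 (1.12 to 2.09) | 0.58 (0.48 to 0.89) |
| 6 vs 0 | not finite | 2.04 | 0.49 |
| 5 vs 5 | 1.00 | 1.00 | 1.00 |

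**Ceiling.** With Yes first and the BI 695501 column, the numerator a/(a+c) cannot exceed 1. For rare events in equal arms the denominator b/(b+d) is close to 0.5. The output therefore cannot go much above 2, however large the true ratio.

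**Would swapping the variables be enough?** Not if No remains the first column, because the result is then the ratio of non-event risks. For 6 versus 2 it is (144/150)/(148/150) = 0.97; for 10 versus 2 it is (140/150)/(148/150) = 0.95. With treatment in the rows, BI 695501 first and the AESI=Yes column read, the code returns the defined ratio in every case.

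**Level order.** The SAP does not state the values or order of AESI_WITH_CRITERION. SAP 15.1.3.1 uses an N level for other flags, and SAP Appendix 1 says that "The trial drug should appear first in tables with treatments as columns". These make a No-first, BI-first table possible but do not establish it.

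**The case against.** The strongest reply is that little depends on this ratio. The definition is written out term by term and is correct, so a programmer who checked output against it would notice the discrepancy. Protocol Section 7.3.4 makes the safety analyses descriptive, with no hypothesis testing. The score test of a ratio of 1 is unchanged by transposing a 2x2 table, and in the examples above all versions agree on whether the interval excludes 1. The AESI counts are illustrative, the intervals are asymptotic, and reversal depends on a level order that the SAP does not give.

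All of that stands, and it limits the weight of the point. It does not remove the mismatch: the SAP supplies this code for use, and run as written it does not estimate the defined ratio. Agreement on excluding 1 is also limited comfort. For 10 versus 2 with No first, the interval excludes 1 from below when the excess is on BI 695501. Balanced counts give 1.00 under every order, so a test run on balanced data would not expose the fault.

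The missing risk ratio for drug-related AEs is a separate omission. The output templates that SAP Section 8 refers to were not available, so only the silence of the SAP text can be asserted. It adds no weight to the code error.

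**Conclusion.** The concern holds. The code in SAP 16.1.1.2 conditions on AESI status and the definition conditions on treatment. The two agree when the arms have equal AESI proportions, and no level order reconciles them in general. At an assumed 150 per arm, reading the BI 695501 column, defined ratios of 2 to 5 would be reported as about 1.35 to 1.71 with Yes first, or about 0.74 to 0.58 with No first, and the limits would belong to the same wrong quantity. The sizes depend on the illustrative counts; the mismatch itself does not. It should be fixed, but it affects descriptive safety output only and leaves the primary equivalence conclusion untouched.

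**What to change.** In SAP 16.1.1.2, change the table request to `TRT*AESI_WITH_CRITERION` and keep the exact score-based limits. Fix BI 695501 as row 1 and AESI=Yes as the risk column, through ORDER=, formats or COLUMN=, and state that order in the text, because swapping the variables alone is not sufficient.

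Separately, add a sentence applying the corrected analysis to the proportion of patients with drug-related AEs, as the protocol synopsis promises.

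The cost is one or two lines of SAS and two sentences in the SAP. No new data are needed.

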16.1.2. ALL TEAEs

Number of subjects, percentages, and number of events overall and for period 1 will be presented by System Organ Class (SOC) and Preferred Term (PT) and also broken down further by maximum intensity and relationship to trial medication.

16.1.2.1. Intensity

Intensity is classed as mild/ moderate/ severe (increasing intensity). TEAEs starting after the first dose of trial medication with a missing severity will be classified as severe. If a subject reports a TEAE more than once within that SOC/ PT, the AE with the worst case intensity will be used in the corresponding severity summaries.

16.1.2.2. Relationship to Trial Medication

A related AE is defined as a TEAE with the item “Causal Relationship between the event and the trial drug” ticked “Related” on the AE form of the eCRF according to the investigator.

TEAEs with a missing relationship to trial medication will be regarded as related to trial medication. If a subject reports the same TEAE more than once for the given period within that SOC/ PT, the TEAE with the worst case

Document: \\ieedc-nas01a:\Boehringer_Ingelheim\BI_695501\XXA39605\Biostatistics\Documentation\SAP\15
-v2.0\BI 1297.12 SAP v2.0 31JAN2018.docx

Author: Version Number: 2.0
Version Date: 31JAN2018

Template No: CS_TP_BS016 Revision 4
Effective Date: 01Apr2016

Reference: CS_WI_BS005

relationship to trial medication within that period will be used in the corresponding relationship summaries.

All drug related AEs will be listed.

16.1.3. TEAEs LEADING TO DISCONTINUATION OF TRIAL MEDICATION

TEAEs leading to permanent discontinuation of trial medication will be identified by using the “Action taken with trial drug due to AE” equal to “Drug Withdrawn” from AEs eCRF pages.

The number and percentages of subjects with TEAEs leading to permanent discontinuation of trial medication will be prepared overall and for period 1 by SOC and PT.

The AEs causing treatment modification or drug withdrawal will be listed.

16.1.4. SERIOUS ADVERSE EVENTS

Serious adverse events (SAEs) are those events recorded as “Serious” on the Adverse Events page of the eCRF. A summary of serious TEAEs by SOC and PT will be prepared overall and for period 1 including the number of subjects, percentages and number of events.

Non-Serious TEAEs with incidence in preferred terms strictly greater than 5% in at least one of treatment groups by SOC and PT will also be displayed overall and for period 1.

A summary of related SAEs by SOC and PT will also be prepared overall and for period 1.

The SAEs and Non-SAEs will be listed.

16.1.5. ADVERSE EVENTS LEADING TO DEATH

TEAEs leading to Death are those events which are recorded as “Fatal” on the Adverse Events page of the eCRF. A summary of TEAEs leading to death by SOC and PT will be prepared overall including the number of subjects, percentages and number of events.

16.1.6. OTHER SAFETY ENDPOINTS AND ADVERSE EVENTS OF SPECIAL INTEREST

A summary of the number of subjects, percentages, and number of events within each of the categories described in the sub-section below will be provided by SOC and PT.

The below table describes the allocation of adverse events to AESI group and Other safety endpoints group:

Adverse Event :	AESI	Other safety endpoint
-----------------	------	-----------------------

Document: \\ieedc-nas01a:\Boehringer_Ingelheim\BI_695501\XXA39605\Biostatistics\Documentation\SAP\15-v2.0\BI 1297.12 SAP v2.0 31JAN2018.docx

Author: Version Number: 2.0
Version Date: 31JAN2018

Template No: CS_TP_BS016 Revision 4
Effective Date: 01Apr2016

Reference: CS_WI_BS005

Serious infections	√	√
Hypersensitivity reactions	√	√
Drug induced liver injury	√	√
Injection site reactions		√
Anaphylactic reactions	√	√

16.1.6.1. Reported by Investigator

AESI reported by Investigators are those events recorded as “Adverse Event of Special Interest” equal to “Yes” on the Adverse Events page of the eCRF.

AESI reported by investigators and CTP specified are detailed in the following sections.

16.1.6.2. Serious Infections

Infections are those events with a SOC equal to “Infections and infestations”.

Serious infections are:

- AEs which are both infections and SAEs as reported on the Adverse Events page of the eCRF.
- AEs which are both infections and identified by the medical advisor as requiring class IV (intravenous) antibiotics.

Serious infection events of special interest (Serious infection AESI) are those events both identified as serious infection adverse events and recorded as “Adverse Event of Special Interest” equal to “Yes” on the Adverse Events page of the eCRF.

Infections and Serious Infections will be summarized. Infections / Serious Infections will also be listed. The listing will include the “Adverse Event of Special Interest” equal to “Yes” information from the Adverse Events page of the eCRF as a flag.

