5.1.2 Secondary Endpoints

Secondary endpoints are:

Efficacy

- Proportion of patients with a PASI 75 response at Week 24
- Mean percentage improvement in PASI at Week 16
- Proportion of patients with a sPGA \leq 1 (clear or almost clear) at Week 16
- Proportion of patients achieving a Dermatology Life Quality Index (DLQI) of 0 or 1 at Week 16

Safety

- Proportion of patients with drug-related AEs

Safety

- Proportion of patients with AEs, SAEs and AEs of Special Interest (AESIs) (e.g., serious infections and hypersensitivity reactions);

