Medical and scientific judgement should be exercised in deciding whether other situations should be considered serious reactions, such as important medical events that might not be immediately life threatening or result in death or hospitalization but might jeopardize the patient or might require intervention to prevent one of the other outcomes listed above. Examples of such events are intensive treatment in an emergency room or at home for allergic bronchospasm, blood dyscrasias or convulsions that do not result in hospitalization or development of dependency or abuse. Any suspected transmission via a medicinal product of an infectious agent is also considered a serious adverse reaction.

AEs considered “Always Serious”

Cancers of new histology and exacerbations of existing cancer must be reported as a serious event regardless of the duration between discontinuation of the drug and the occurrence of the cancer.

In accordance with the European Medicines Agency initiative on Important Medical Events, BI has set up a list of further AEs, which by their nature, can always be considered to be “serious” even though they may not have met the criteria of an SAE cited above.

A copy of the latest list of “Always Serious AEs” can be found in the ISF and eCRF. These events should always be reported as SAEs as described above.

Adverse events of special interest

The term AESI relates to any specific AE that has been identified at the project level as being of particular concern for prospective safety monitoring and safety assessment within this trial, e.g., the potential for AEs based on knowledge from other compounds in the same class.

AESI need to be reported to the sponsor's/sponsor designee Pharmacovigilance Department within the same timeframe that applies to SAE, please see above.

The following are considered as AESIs:

1. Hepatic injury

A hepatic injury is defined by the following alterations of hepatic laboratory parameters:

- an elevation of AST and/or ALT \geq 3-fold ULN combined with an elevation of total bilirubin \geq 2-fold ULN measured in the same blood draw sample, and/or
- marked peak aminotransferase (ALT, and/or AST) elevations \geq 10-fold ULN

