These lab findings constitute a hepatic injury alert and the patients showing these lab abnormalities need to be followed up according to the "DILI checklist" provided in the ISF. In case of clinical symptoms of hepatic injury (icterus, unexplained encephalopathy, unexplained coagulopathy, right upper quadrant abdominal pain, etc.) without lab results (ALT, AST, total bilirubin) available, the Investigator should make sure these parameters are analyzed, if necessary in an unscheduled blood test. Should the results meet the criteria of hepatic injury alert, the procedures described in the DILI checklist should be followed.

2. Anaphylactic reactions

3. Serious infection (defined as infections requiring IV antibiotics or meeting the regulatory definition of a SAE)

4. Hypersensitivity reactions

Intensity of AEs

The intensity of the AE should be judged based on the following:

Mild:	Awareness of sign(s) or symptom(s) that is/are easily tolerated
Moderate:	Sufficient discomfort to cause interference with usual activity
Severe:	Incapacitating or causing inability to work or to perform usual activities

Causal relationship of AEs

The definition of an adverse reaction implies at least a reasonable possibility of a causal relationship between a suspected medicinal product and an AE. An adverse reaction, in contrast to an AE, is characterised by the fact that a causal relationship between a medicinal product and an occurrence is suspected.

Medical judgment should be used to determine the relationship, considering all relevant factors, including pattern of reaction, temporal relationship, de-challenge or re-challenge, confounding factors such as concomitant medication, concomitant diseases and relevant history.

Arguments that may suggest that there is a reasonable possibility of a causal relationship could be:

- The event is consistent with the known pharmacology of the drug
- The event is known to be caused by or attributed to the drug class.
- A plausible time to onset of the event relative to the time of drug exposure.
- Evidence that the event is reproducible when the drug is re-introduced
- No medically sound alternative aetiologies that could explain the event (e.g., pre-existing or concomitant diseases, or co-medications).
- The event is typically drug-related and infrequent in the general population not exposed to drugs (e.g., Stevens-Johnson syndrome).

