16.1.6.3. Hypersensitivity Reactions

Hypersensitivity reactions are those events recorded as MedDRA code in the pre-defined Standardized MedDRA Queries (SMQ) “Hypersensitivity” (narrow).

Hypersensitivity reaction adverse events of special interest (Hypersensitivity reactions AESI) are those events both identified as Hypersensitivity reaction adverse events and recorded as “Adverse Event of Special Interest” equal to “Yes” on the Adverse Events page of the eCRF.

Hypersensitivity reactions will also be listed. The listing will include the “Adverse Event of Special Interest” equal

Document: \\ieedc-nas01a:\Boehringer_Ingelheim\BI_695501\XXA39605\Biostatistics\Documentation\SAP\15-v2.0\BI 1297.12 SAP v2.0 31JAN2018.docx

Author: Version Number: 2.0
Version Date: 31JAN2018

Template No: CS_TP_BS016 Revision 4
Effective Date: 01Apr2016

Reference: CS_WI_BS005

to “Yes” information from the Adverse Events page of the eCRF as a flag.

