16.1.6.6. Anaphylactic reactions

Anaphylactic reactions are those events recorded as MedDRA code in the pre-defined Standardized MedDRA Queries (SMQ) = “Anaphylactic reactions” (narrow)

Anaphylactic reaction adverse events of special interest (Anaphylactic reaction AESI) are those events both identified as Anaphylactic reactions and recorded as “Adverse Event of Special Interest” equal to “Yes” on the Adverse Events page of the eCRF.

Anaphylactic reactions will also be listed. The listing will include the “Adverse Event of Special Interest” equal to “Yes” information from the Adverse Events page of the eCRF as a flag.

Document: \\eedc-nas01a:\Boehringer_Ingelheim\BI_695501\XXA39605\Biostatistics\Documentation\SAP\15
-v2.0\BI 1297.12 SAP v2.0 31JAN2018.docx

Author: Version Number: 2.0
Version Date: 31JAN2018

Template No: CS_TP_BS016 Revision 4
Effective Date: 01Apr2016

Reference: CS_WI_BS005

16.1.7. AES OCCURRING AFTER THE LAST INJECTION FOR SUBJECTS DISCONTINUED DUE TO LACK OF EFFICACY

Subjects who discontinued treatment due to lack of efficacy will be identified from “End of treatment visit” eCRF page, where “Reason for End of Treatment” is “Lack of Efficacy”.

Number of subjects, percentages, and number of events occurring after the last injection and prior to the last injection + 10 weeks for subjects discontinued due to lack of efficacy by SOC and PT will be prepared.

AEs occurring after the last injection and prior to the last injection + 10 weeks for subjects discontinued due to lack of efficacy will be listed.

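### The SAP counts an event in an AESI category only if the investigator also ticked the AESI item, so unticked serious infections and hepatic injuries that are AESIs under the protocol miss the AESI counts and risk ratio

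*SAP*

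**What the plan says.** **Protocol.** Section 5.3.6.1 introduces its list with "The following are considered as AESIs" and names four kinds of event: hepatic injury, anaphylactic reactions, serious infection and hypersensitivity reactions. Two are given objective criteria. For the liver, "A hepatic injury is defined by the following alterations of hepatic laboratory parameters", followed by transaminase and bilirubin thresholds. The infection entry is "Serious infection (defined as infections requiring IV antibiotics or meeting the regulatory definition of a SAE". An eCRF tick is not part of any entry. Section 5.1.2 lists among the safety endpoints "Proportion of patients with AEs, SAEs and AEs of Special Interest (AESIs".

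**SAP.** Section 16 carries the same endpoint: "Proportion of patients with AEs, SAEs, and AESIs". Section 16.1.6.1 defines investigator-reported AESIs by the eCRF AESI item alone. The category sections then require both conditions. Serious-infection AESIs "are those events both identified as serious infection adverse events and recorded as" AESI = Yes (16.1.6.2). Hypersensitivity AESIs "are those events both identified as Hypersensitivity reaction adverse events and recorded as" AESI = Yes (16.1.6.3). Anaphylaxis AESIs "are those events both identified as Anaphylactic reactions and recorded as" AESI = Yes (16.1.6.6). Section 16.1.6.4 words drug-induced liver injury the same way, after selection by the medical advisor. Section 16.1.1.2 computes a risk ratio with exact 95% CI whose numerators are the subjects with an AESI in each arm.

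**The concern.** Under the protocol, a patient hospitalised for pneumonia has an AESI because the event is an infection meeting SAE criteria. Under SAP 16.1.6.2 the same event is a serious-infection AESI only if someone at the site also set the AESI item to Yes. The AESI figures then depend on how completely the item was filled in as well as on how often the events occurred.

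The proportion of patients with AESIs is a stated safety endpoint, and 16.1.1.2 specifies a risk ratio for it in a SAP that otherwise plans no between-group safety comparison unless a section says so. In a biosimilar comparison, readers will look at those figures. The SAP has no step that reconciles qualifying but unticked events, and no AESI analysis on the protocol definition alone.

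**Working it through.** The documents state no AESI rate or AESI risk ratio, so there is no figure of the plan's to reproduce. The check is a comparison of rules, followed by an illustration on assumed counts.

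**1. Rule against rule**

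| Category | Protocol 5.3.6.1 | SAP, to count as a category AESI |
|---|---|---|
| Serious infection | IV antibiotics or SAE criteria | Infections SOC, and SAE or IV antibiotics per medical advisor, and tick (16.1.6.2) |
| Hepatic injury | Laboratory thresholds only | An AE picked out by the medical advisor in a patient with potential DILI laboratory findings, and tick (16.1.6.4) |
| Hypersensitivity | Named, no coded definition | Narrow SMQ and tick (16.1.6.3) |
| Anaphylaxis | Named, no coded definition | Narrow SMQ and tick (16.1.6.6) |

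The hepatic route differs in one more way. For patients with impaired liver function at baseline, SAP 16.3.1 replaces the ULN by the baseline value in the combined transaminase and bilirubin criterion. The protocol thresholds are multiples of the ULN for everyone.

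**2. Where an unticked qualifying event goes.** It fails the tick-only set (16.1.6.1) and the category sets (definition and tick). The code in 16.1.1.2 uses a variable, AESI_WITH_CRITERION, that the SAP does not define. Whichever of these sets it holds, the event is not in the numerator. The allocation table in 16.1.6 places the four categories in the AESI column without mentioning the tick, but the sub-sections that define the AESI version of each category all require it.

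**3. Illustration of size.** Inputs: about 300 patients randomised 1:1 (SAP 3.1), so n = 150 per arm. The AESI counts and the share ticked, s, are assumptions. The ratio follows 16.1.1.2: RR = (a/150)/(c/150). For simplicity the CI is log-normal instead of the SAP's exact interval: exp[ln RR ± 1.96·√(1/a − 1/150 + 1/c − 1/150)].

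| Assumed true counts | s, both arms | Counted | Proportions | RR (95% CI) |
|---|---|---|---|---|
| 10 v 10 | 1.0 | 10 v 10 | 6.7% v 6.7% | 1.00 (0.43–2.33) |
| 10 v 10 | 0.8 | 8 v 8 | 5.3% v 5.3% | 1.00 (0.39–2.59) |
| 10 v 10 | 0.5 | 5 v 5 | 3.3% v 3.3% | 1.00 (0.30–3.38) |
| 12 v 6 | 1.0 | 12 v 6 | 8.0% v 4.0% | 2.00 (0.77–5.19) |
| 12 v 6 | 0.5 | 6 v 3 | 4.0% v 2.0% | 2.00 (0.51–7.85) |

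For the second row: √[2 × (1/8 − 1/150)] = 0.486, and exp(±1.96 × 0.486) gives 0.39 and 2.59. With the same s in both arms, s cancels from the ratio. The proportions shrink by the factor s and the interval widens.

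**The case against.** The best defence is that little is hidden. All four categories are also other safety endpoints in the 16.1.6 table, summarised without the tick. The listings show every category event with the tick as a flag. The hospitalised infection also appears in the serious TEAE tables (16.1.4), and liver cases are counted from laboratory data as possible Hy's law and possible DILI (16.3). Investigators must report AESIs on the same 24-hour timeline as SAEs (Protocol 5.3.6.2), so ticking may be nearly complete. AESIs are listed under other safety endpoints, safety is descriptive, and no decision rests on the count. All of this stands. It limits the consequence, but it does not make the AESI figures match the protocol definition.

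A reader might infer more than the documents support, in three ways:

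- **That the risk ratio is biased because ticking differs by arm.** Safety assessments are made by blinded personnel (Flow Chart, note 3). Unblinded pharmacists and administrators are barred from safety evaluations (Appendix 10.3), and third-party blinding is only a contingency (Protocol 4.1.5.1). Nothing gives a basis for different ticking rates.
- **That ticked events outside the SMQ vanish from AESI reporting.** They remain in the investigator-reported set of 16.1.6.1; only the category label is lost.
- **That the double condition must undercount protocol AESIs in every category.** The narrow SMQ is the SAP's search tool, and the protocol gives no coded definition of hypersensitivity or anaphylaxis. An unticked SMQ match is therefore not always a protocol AESI.

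**Conclusion.** The point holds. In four sections the SAP makes the tick a condition of a category AESI, and the protocol does not. For serious infection and hepatic injury the mismatch is plain, because the protocol criteria can be applied without the tick. For hypersensitivity and anaphylaxis it is a matter of an undefined protocol term and a SAP search.

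The size cannot be computed. It rests entirely on the share of qualifying events left unticked, which neither document gives and which may be small. Under-ticking that is equal between arms lowers the AESI proportions and the precision of the ratio, but not its expected value. The primary efficacy analysis and the secondary safety endpoint (drug-related AEs) are unaffected. So are injection-site reactions (16.1.6.5), which are not AESIs and carry no tick condition.

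**What to change.** In the SAP:

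1. Define serious-infection AESIs (16.1.6.2) and hepatic-injury AESIs (16.1.6.4) by the Protocol 5.3.6.1 criteria, whatever the tick. For the liver this means the protocol's ULN-based thresholds.
2. For hypersensitivity (16.1.6.3) and anaphylaxis (16.1.6.6), drop the tick as a requirement and count narrow-SMQ events. Have ticked events outside the SMQ assigned to a category at blinded medical review. The only documented eCRF item is one Yes/No field, so the category cannot be derived from it.
3. State that these sets feed the AESI proportion and the 16.1.1.2 risk ratio, and define the code variable accordingly.
4. Keep the tick as a listing flag, present the tick-only count as supplementary, and query discordant events before lock.

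The cost is SAP wording, re-derivation of existing variables and a short medical review. No new data are needed beyond the answers to queries. AESI counts will be slightly higher, and some SMQ matches may be less specific than events that an investigator flagged.
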